Anesthesia will be characterized as general, neuraxial, or combined. Use of peripheral plane and nerve blocks will also be recorded. Routine anesthetic variables will be recorded including time-weighted average volatile anesthetic partial pressure, fluid type and volume, estimated blood loss, and transfusions. Postoperative opioids will be converted to morphine sulphate equivalents (Appendix 3).⁴³ On an as-available basis, we will record hemoglobin and troponin concentrations obtained during the initial four postoperative days.

Outcome definitions

Initial phase

Primary Aim. As in previous studies,^{5,44} we will present vital sign abnormalities as continuous functions of duration and severity of vital sign abnormalities. An advantage of this approach is that we do not need to pre-define thresholds and will instead present various combinations of durations and thresholds for bradycardia, tachycardia, saturation, and respiratory rate. See Figure 2 as an example for saturation.

However, to evaluate clinical detection of vital sign abnormalities we need to define thresholds. We will consider the following thresholds and continuous durations to be clinically meaningful: A) saturation <90% for 30 minutes; B) heart rate >110 beats/min for 30 minutes; C heart rate <40 beats/min for 15 minutes; D) respiratory rate <6/minute for 30 minutes or <3/minute for 10 minutes; and, E) respiratory rate >20 for 30 minutes. Because physiological signals are inherently noisy, all values will be electronically smoothed to some degree, but raw data summaries will be used as a cross-check (see Data Analysis for details).

Secondary Aim 2. Continuous ward monitoring with the GE Portrait Mobile Monitoring Solution detects a composite of vital sign abnormalities more often than routine nursing vital signs at 4-hour intervals in noncardiac surgical patients over the initial 72 postoperative hours in the surgical ward while hospitalized. Components of the composite will be: A) saturation <85% for \geq 60 seconds,⁵ B) pulse rate <130 beats/min for 30 secs,⁴⁵ C) pulse rate <40 beats/min for 30 secs,⁴⁶ D) low respiratory rate <4/minute for 30 secs E) high respiratory rate >25 for 120 secs, and, F) apnea >120 secs.

Phases 2 and 3

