For the raw data, we will conduct two analyses: **First**, to assess the overall exposure to hypoxemia for each patient, we will summarize the distribution of number of hypoxic minutes per hour of monitoring using incidence curves. Various thresholds defining hypoxemia will be used to generate the incidence curves. **Second**, we will use quantile regression⁴⁷ to characterize the median, quartiles, 10th and 90th percentiles, and 5th and 95th percentiles of the distribution of SpO₂ across patients as a function of postoperative time. Nonlinearities in these quantile curves will be taken into account by incorporating restricted cubic splines for the time variable in the quantile regression models.

For the analyses of filtered SpO_2 data, we will smooth each individual patient's SpO_2 -versus-time profile using a Gaussian kernel smoother (i.e., the smoothed estimate of SpO_2 for a specific time point will be a weighted average of the surrounding SpO_2

values, where the weights will be determined according to a Gaussian distribution centered at that time point with an inter-quartile range of 3 hours). Using the smoothed profiles, we will then estimate the incidence of hypoxic episodes of varying duration under a range of SpO₂ thresholds characterizing hypoxemia.

Phase I

Primary Aim. Collect blinded data to evaluate the frequency and duration of vital sign abnormalities detected by the GE Portrait monitor, the fraction that are detected clinically, and the overlap between them. We will use descriptive statistics such as median [quartiles] and mean (SD) to summarize clinical detection of vital sign abnormalities using the definitions given in Outcome Definitions using both the raw data and also using the data smoothing techniques described above. Raw data summaries will be helpful so that truly extreme values are not routinely "smoothed away" in the algorithms described in Data Analysis.

Secondary Aim 1. We will design clinically meaningful alerts based on the data collected and abnormalities detected, while avoiding false alerts. This will involve estimating sensitivity and specificity for detecting true abnormalities across the range of possible alert cut-points and choosing cut-points which maximize both sensitivity and specificity. Accuracy, along with positive and negative predictive values, will be reported. All estimates will be reported with confidence intervals.

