We plan for 100 patients in the first phase, 150 in phase 2, and 250 in phase 3. When comparing groups on continuous outcomes for Phases 1, 2 and 3, respectively, we will have 90% power at the 0.05 significance level to detect a difference in means of 0.66, 0.53 and 0.41. When comparing groups on binary outcomes such as the collapsed composite outcome in Phase III we will have 90% power at the 0.05 significance level to detect relative risks of 0.10, 0.30 or 0.45 or stronger given corresponding control group incidences of 0.10, 0.20 or 0.30.

Limitations

Active participation and engagement from ward clinicians will be essential, including nurses, hospitalists, anesthesiologist members of the acute pain team, and surgeons. To that end, key personnel from each specialty are co-investigators and have agreed to champion the project, including the Associate Chief Nursing Officer for Nursing Research and a senior member of a relevant surgical department. Thus, while considerable effort will be required, we anticipate high engagement from participating clinicians.

Our experience with four other continuous ward monitoring systems is that most patients tolerate monitoring well, but there are inevitably patients who drop out of monitoring studies. And even for those who remain in a study, there are often gaps of varying duration. Our experience is that paying patients, even a trivial amount, much improves cooperation with monitoring. The GE Portrait system is untethered and small, and therefore should be relatively well tolerated.

Clinical interventions are multifactorial and usually based on many factors. It will thus not always be possible to reliably attribute a particular intervention to a GE Portrait alert. Nonetheless, by personally asking clinicians in real time, we will reasonably be able to estimate whether the GE Portrait alert was the initial prompt for further evaluation and eventual treatment.

Human Subjects Protection

In all cases, good judgement will predominate. Clinicians should always act in their patients' best interests, irrespective of this protocol.

The study will be conducted with IRB approval and written patient consent. The study will be restricted to designated wards because active nursing engagement and training will be required. Furthermore, the GE monitoring system will only be available in selected wards.

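### The Phase 1 duration-based definitions (A–E) are not measured reliably on either planned signal: the raw version has no interruption or gap rule, and the only specified smoother is far too wide

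*Combined protocol and SAP*

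**What the plan says.** Outcome definitions, Initial phase, Primary Aim, first says that abnormalities will be shown over many combinations of threshold and duration. Fixed thresholds are introduced only to judge clinical detection: "We will consider the following thresholds and continuous durations to be clinically meaningful: A) saturation <90% for 30 minutes", followed by B to E for heart rate and respiratory rate, with durations of 10, 15 or 30 minutes. The same paragraph adds: "Because physiological signals are inherently noisy, all values will be electronically smoothed to some degree, but raw data summaries will be used as a cross-check".

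Data analysis, Phase I, Primary Aim, then summarises clinical detection "using the definitions given in Outcome Definitions using both the raw data and also using the data smoothing techniques described above". It explains that raw summaries are kept so that extreme values are not lost to smoothing.

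The only smoother described is a Gaussian kernel for saturation, "centered at that time point with an inter-quartile range of 3 hours". None is described for heart rate or respiratory rate.

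Limitations says of patients who stay in monitoring: "And even for those who remain in a study, there are often gaps of varying duration". The document does not state the sampling interval, how long an interruption may last without ending a run, how a gap inside a run is treated, or which version prevails if raw and smoothed counts differ.

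**The concern.** A rule that needs an unbroken run is sensitive to single samples. A patient whose true saturation sits slightly below 90% for an hour will give some readings at or above 90% through noise alone. If each one restarts the clock, the hour becomes several short runs and no episode. Lost samples do the same whatever the depth of the desaturation.

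Smoothing is the natural protection, but a kernel spread over hours flattens a 30-minute event almost completely. The two planned versions thus fail by opposite mechanisms, and nothing in between is specified.

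At stake is the set of episodes from which the clinically detected fraction, part of the Phase 1 primary aim, is calculated. If that set is decided by sampling interval and signal noise, the fraction describes the device settings and the programmer's choices as well as the patients.

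**Working it through.** The plan gives no figure for the share of episodes captured, so there is nothing to reproduce.

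**Inputs from the document.** Definition A (below 90% for a continuous 30 minutes); kernel inter-quartile range of 3 hours.

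**Inputs assumed, because the document gives none.** Noise SD 1 to 2 saturation points; correlation time 1 to 5 minutes; 10-second samples recorded as whole percentages; baseline saturation 92% or 95%; random loss of 1% or 2% of samples.

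**1. Raw rule, independent noise.** For a true 30-minute episode lying m points below the limit, with noise SD s and N samples in 30 minutes, the probability of an unbroken run is Φ(m/s)^N. Take m = 2, s = 1 and no rounding:
- 10-second samples: 0.97725^180 = 0.016.
- 60-second samples: 0.97725^30 = 0.50.

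The same patient state gives very different counts when only the sampling interval changes.

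**2. Raw rule, correlated noise.** First-order autoregressive simulation of a true 60-minute episode (360 samples). The entries are the share containing a 30-minute run below 90%. Each range spans correlation times of 1 to 5 minutes; for the raw rule the low end is the 1-minute value, and for the medians the low end is the 5-minute value.

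| True level, noise SD | Literal raw rule | Non-overlapping 5-minute medians |
|---|---|---|
| 86%, SD 1 | almost always | – |
| 87%, SD 1 | 88–98% | – |
| 87%, SD 1.5 | 20–74% | 99–100% |
| 87%, SD 2 | 2–46% | 94–99% |
| 88%, SD 1 | 10–62% | – |
| 88%, SD 1.5 | 0.5–32% | 84–97% |

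In the last row the expected share of samples below 90 is Φ((89.5 − 88)/1.5) = Φ(1) = 84%, because values round to 90 from 89.5 upward. Yet the raw rule usually records no episode.

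**3. Lost samples, no noise.** If a missing sample ends the run, the chance of at least one run of 180 in 360 samples with loss rate q is (1 − q)^180 × (1 + 180q).
- q = 1%: 0.164 × 2.8 = 0.46.
- q = 2%: 0.0263 × 4.6 = 0.12.

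**4. Smoothed rule.** The kernel SD is 3/1.349 = 2.22 hours. An isolated episode of length L hours has weight w = 2Φ(L/(2 × 2.22)) − 1 at its centre. To bring the smoothed value below 90% from baseline b, the true level must fall to b − (b − 90)/w.
- L = 0.5: w = 0.0895. From 95%, 95 − 5/0.0895 = 39%; from 92%, 92 − 2/0.0895 = 70%.
- L = 1: w = 0.178. 67% and 81%.
- L = 3: w = 0.50. 85% and 88%.

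The kernel suits desaturation lasting hours and all but removes an isolated 30-minute episode.

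**5. Cost of using medians.** With 5-minute medians, a true hour at 91% with SD 2 is falsely counted in at most about 2% of cases. A true hour at exactly 90% with SD 2 is counted in up to about 10%. Window length matters: at 88% with SD 1.5, 1-minute medians recover only 30–57%.

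**The case against.** The strongest reply is that the plan already recognises noise. It says values will be smoothed and makes raw data a cross-check, and Data analysis admits that lingering mild desaturation is hard to see in raw saturation. Restarting the clock at one sample is a literal reading of the word continuous, not a stated algorithm. Phase 1 is a descriptive pilot of 100 patients, and Methods promises a full statistical analysis plan before any data are evaluated, where coding rules would belong. All of this is correct. It does not remove the point, because the only smoothing actually specified cannot see a 30-minute event, none is given for heart rate or respiratory rate, and no other coding of the raw rule is offered.

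Several stronger readings are tempting and are not supported:
- **That the definitions require raw data.** They do not; raw is one of two versions.
- **That most true 30-minute episodes are missed on raw data.** Under the assumed noise this holds only within about 1 noise SD of the limit. Further below, the result depends on inputs the document omits.
- **That the raw cross-check fails its purpose.** Its stated purpose is to preserve extreme values, and extreme-value summaries do not need a run.
- **That alert design rests on these counts.** Secondary Aim 1 searches over a range of alert cut-points, and nothing ties it to raw A–E counts.
- **That the detected fraction is biased in a known direction.** Missed episodes leave both numerator and denominator, and no direction has been shown.

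**Conclusion.** The concern holds in a limited form. Definitions A–E cannot be applied reliably as written on either planned signal. On raw data the loss is concentrated near the threshold: from near-total to about a third of 60-minute episodes counted at 88% with SD 1.5, against almost no loss at 86% with SD 1. On smoothed data an isolated 30-minute desaturation carries about 9% weight and is effectively invisible, whatever the noise.

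The raw figures rest on assumed noise SD, correlation time and sampling interval, and on a literal coding of the run. Only saturation was calculated. For heart rate and respiratory rate the point is the missing specification, not a measured loss.

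The effect is confined to the clinical-detection summaries that use A–E. Hypoxic minutes per hour, the quantile regression and the extreme-value summaries do not depend on unbroken runs. This should be settled before Phase 1 data are analysed; it is not a reason to redesign the phase.

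**What to change.** In the analysis plan, before Phase 1 data are evaluated:
- State the sampling or averaging interval of the recorded data for each vital sign.
- Base the main A–E count on medians of valid samples in windows short relative to each duration: about 5 minutes for the 30-minute definitions, shorter for the 10- and 15-minute ones.
- State that a run ends only with a full window back over the limit or a gap longer than one window.
- Apply this to saturation, heart rate and respiratory rate alike, and name it as the primary version.
- Report 1-minute medians and the literal raw rule as sensitivity analyses.
- Keep raw data for extreme-value and minutes-per-hour summaries, and the 3-hour kernel for desaturation lasting hours.

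The cost is a few lines of text and minor programming. The downsides are small: brief true recoveries inside an episode are ignored, and a patient sitting exactly at 90% may be counted in up to about 10% of hours if noise SD is 2.

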Various risk factors for developing respiratory depression have been reported for post-surgical patients including sleep apnea, obesity, snoring, old age, post-surgery, increased opioid dose requirement, concomitant use of other sedating medications, comorbidities like preexisting pulmonary or cardiac disease, use o patient-controlled opioid analgesia, and smoking.^{1,4,7,16,17} Nonetheless, postoperative respiratory events remain difficult to predict. For example, we have shown that STOP-BANG scores (a measure of obstructive sleep apnea risk) are not associated with the amount of postoperative oxygen desaturation (**Fig. 3**).⁷ Similarly, risk was not reduced by using short-acting opioids in patient controlled analgesia systems (**Fig. 4**).⁸

In PRODIGY there was some relationship between baseline and procedural characteristics, but respiratory events could not be reliably predicted, with area under the receiver-operating characteristics curve of only 0.7. Available information thus indicates that it is difficult to reliably predict which postoperative inpatients will desaturate, or the severity of their hypoxemia. A corollary is that all patients need to be continuously monitored to reliably detect respiratory compromise early enough to intervene effectively and presumably prevent serious complications.

The role of opioids

Opioid analgesia remains the primary pharmacologic intervention for managing pain in hospitalized patients.¹⁹ However, up to 80% of patients who received opioid analgesics experience Opioid-Related Adverse Drug Events (ORADEs).⁴ The Joint Commission on Hospital Accreditation identifies improper patient monitoring as one of the main causes of ORADEs.^{1,5}

Opioid-induced respiratory depression is traditionally defined using surrogate measures, such as hypoventilation with or without oxygen desaturation, and is often a diagnosis of exclusion¹⁰ and is probably much under-estimated.^{11,12} Opioid-related adverse events, including respiratory depression, are associated with increased length of stay (mean five additional days), readmission (15.8% vs 9.4% in patients without events), and cost (mean increase \$10,000).¹³

Preventing respiratory complications

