The patient units are powered by small rechargeable batteries that last at least 24 hours. Investigators will swap depleted batteries for fully charged ones daily. Data from the patient module will be transmitted to a small hub in each patient's room using MBAN (similar to Bluetooth) proprietary secure communication. The hub normally rests in a charging dock, and can be taken with patients if they care to leave their rooms. The hub retransmits monitor data in real time via the hospital's secure "internal" Wi-Fi system to display screens in clinical areas and to the Department of Outcomes Research, which is a double-locked card-key controlled location restricted to Departmental investigators.

During the initial phase of the study, all monitoring will be clinician-blinded. That is, recorded for *post hoc* analysis. During the subsequent phases of the study, patients will be randomly assigned to unblinded versus blinded monitoring. In both cases, information from the GE Portrait Monitor will be recorded, but will be available to clinicians only when patients are assigned to unblinded monitoring. Randomization will be based on computer-generated codes, in random blocks of 4-8 patients, without stratification. A web-based system will be accessed by investigators after consent is obtained. Allocation will therefore be concealed as long as practical.

Measurements

Baseline demographic and morphometric characteristics will be recorded, including height, weight, and sex. Elements of the STOP-BANG sleep apnea questionnaire will be recorded.^{7,41,42} Cardiopulmonary risks will be recorded, including hypertension requiring treatment, diabetes requiring oral medications or insulin, history of previous myocardial infarction, congestive heart failure, chronic obstructive pulmonary disease, current smoking status, and pack-years of smoking history. Cardiovascular and pulmonary medications will be similarly recorded by category, including beta blockers,

angiotensin converting enzyme inhibitors, angiotensin receptor blockers, calcium channel blockers, statins, bronchodilators, and inhaled steroids.

Baseline laboratory values (within 30 days before surgery) will be recorded on an as-available basis, including albumin, BNP, NT-ProBNP, troponin, and FEV1. Results of sleep studies will be recorded.

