Secondary Aim 2. We will determine the optimal frequency of the alerts, using criteria determined in Secondary Aim 1. This will be largely descriptive, but will involve a tradeoff between increasing the frequency of alerts and the corresponding loss to sensitivity and specificity.

Secondary Aim 3. We will estimate the proportion and corresponding confidence interval of potentially serious vital sign abnormalities detected by GE Portrait monitoring that are also detected by clinicians using routine every four-hour monitoring, and vice versa.

Phase II

Primary Aim. We will assess the treatment effect of unblinded continuous ward monitoring versus blinded monitoring on the cumulative duration of the various vital sign abnormalities using parametric (e.g., s-sample t-test) or non-parametric (e.g., Wilcoxon-Mann-Whitney test), as appropriate.

Secondary Aim. In the unblinded group we will evaluate the fraction of alerts from the GE Portrait monitor that clinicians designate dichotomously as clinically meaningful. Results will be presented as a percentage with 95% confidence intervals.

Phase III

Primary Aim. We will test whether and estimate the extent to which unblinded continuous ward monitoring with the GE Portrait Mobile Monitoring Solution reduces the time with

vital sign abnormalities as defined in the initial phase of the study using statistical methods similar to those described in the primary aim for Phase II above.

Exploratory Aim 1. We will assess whether and the extent to which unblinded continuous ward monitoring of saturation, ventilation, and pulse rate monitoring reduces a collapsed composite of substantive respiratory interventions as described in specific aims using a Chi-Square test and estimating the relative risk and its confidence interval. As a secondary analysis we will assess the treatment effect using a distinct effects generalized estimating equation (GEE) model which estimates a separate treatment effect for each component and then averages them (average relative effect method, ARE).⁴⁸ ⁴⁹ This method prevents components with higher frequency, which also may be less severe, from driving the treatment effect results. It simultaneously accounts for the correlation across components, and allows assessment of the treatment-by-component interaction. Finally, we will estimate the common effect (or "global") treatment effect across the components in a GE model estimating a single effect.

Sample Size Considerations

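### The Phase II and III primary comparison is unadjusted although baseline variables are recorded and ward is known; the test is valid, but a modest gain in precision is forgone

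*Combined protocol and SAP*

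**What the plan says.** All places are in the combined protocol and SAP.

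- **Data analysis, Phase II, Primary Aim.** Unblinded and blinded monitoring are compared on cumulative duration "using parametric (e.g., s-sample t-test) or non-parametric (e.g., Wilcoxon-Mann-Whitney test), as appropriate" (the first test is presumably the two-sample t-test).
- **Data analysis, Phase III, Primary Aim.** The comparison is made "using statistical methods similar to those described in the primary aim for Phase II above".
- **Protocol.** Patients are randomized "in random blocks of 4-8 patients, without stratification". Methods expects two to four wards.
- **Measurements.** Height, weight, sex, heart failure, COPD, smoking and cardiopulmonary drugs are recorded, and "Elements of the STOP-BANG sleep apnea questionnaire will be recorded". None of these has a role in the treatment comparison. Ward is not on the list, but the first eligibility criterion makes it known for every patient.
- **Background on risk factors.** In the earlier capnography and oximetry cohort, baseline and procedural characteristics predicted respiratory events "with area under the receiver-operating characteristics curve of only 0.7". The same paragraph reports that STOP-BANG scores were unrelated to how much patients desaturated.
- **Sample Size Considerations.** "We plan for 100 patients in the first phase, 150 in phase 2, and 250 in phase 3", and "we will have 90% power at the 0.05 significance level to detect a difference in means of 0.66, 0.53 and 0.41".

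**The concern.** In a randomized comparison, adjusting for a few prespecified prognostic variables removes outcome variance that has nothing to do with treatment, and corrects chance imbalance in those variables. The plan has the variables and gives them no such use.

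Ward deserves particular attention. Randomization does not balance it, and the intervention works through ward staff responding to alerts; the Limitations section calls their engagement essential. Ward is therefore plausibly prognostic, and only the analysis can correct a chance imbalance.

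At stake is precision in two small randomized phases that are meant to guide a larger trial. The validity of the planned test is not in question.

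**Working it through.** **Inputs.** From Sample Size Considerations: N = 150 and 250 in Phases II and III, differences 0.53 and 0.41, 90% power, alpha 0.05. Assumed, because the documents do not say: 1:1 allocation (n = 75 and 125 per arm), a two-sided test, differences in SD units, and the R-squared of the covariates for cumulative duration.

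**Step 1: reproduce the plan's figures.** Detectable difference = (1.960 + 1.282) × √(2/n).

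- n = 50: 0.648
- n = 75: 0.529
- n = 125: 0.410

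The t distribution gives 0.655, 0.533 and 0.412. The plan states 0.66, 0.53 and 0.41, so its figures reproduce as unadjusted two-sided comparisons. One-sided values (0.585, 0.478, 0.370) do not match. At the stated differences the noncentrality is 0.53 × √(75/2) = 3.246 and 0.41 × √(125/2) = 3.241. Power of the t-test is then 89.7% and 89.8%.

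**Step 2: power after adjustment, with the covariates paid for.** For k covariate terms in a linear model:

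- noncentrality = d × √(n/2) / √[(1 − R²) × f]
- f = (N − 3)/(N − 3 − k), the expected cost of chance imbalance
- degrees of freedom = N − 2 − k

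For k = 4, f = 147/143 = 1.028 in Phase II and 247/243 = 1.016 in Phase III. Example, Phase II at R² = 0.12: 3.246/√(0.88 × 1.028) = 3.412. Against a critical value of 1.977 on 144 degrees of freedom, power is 92.4%.

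| R² (assumed) | 4 terms, Phase II / III | 7 terms, Phase II / III | 8 terms, Phase II / III |
|---|---|---|---|
| 0 | 88.9% / 89.3% | 88.2% / 88.9% | 88.0% / 88.8% |
| 0.05 | 90.4% / 90.8% | 89.8% / 90.4% | 89.5% / 90.3% |
| 0.12 | 92.4% / 92.7% | 91.8% / 92.4% | 91.6% / 92.3% |
| 0.25 | 95.7% / 95.9% | 95.3% / 95.7% | 95.1% / 95.6% |

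Unadjusted, for comparison: 89.7% / 89.8%.

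The break-even R² is 0.028 / 0.016 with four terms and 0.055 / 0.033 with eight. Ward takes one to three terms for two to four wards, so ward plus three or four baseline terms comes to four to seven.

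**Step 3: where 0.12 comes from.** An AUC of 0.70 corresponds, under a binormal model, to d = √2 × Φ⁻¹(0.70) = 0.742. At the cohort's 46% event rate, d²pq = 0.550 × 0.46 × 0.54 = 0.137, and R² = 0.137/1.137 = 0.12. This gives a sense of scale only, because it describes a binary event and not duration.

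**Step 4: how likely is ward imbalance?** Take two equal wards. The difference between arms in one ward's share has SD √(0.25 × 2/n), which is 0.082 in Phase II and 0.063 in Phase III. A gap of at least 10 points has z = 1.22 and 1.58, so its probability is about 22% and 11%.

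**The case against.** The strongest case against is that the gain may be close to nothing.

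- **The 0.12 is borrowed.** It comes from a 24-hour composite event that included capnography criteria, and procedural variables contributed to the prediction. The trial outcome is time with abnormalities, pulse rate included, over up to 72 hours and under thresholds still to be set. This stands, and it is why a range is shown.
- **The protocol holds contrary evidence.** Amount of desaturation is closer to cumulative duration than a yes/no event is, and STOP-BANG scores did not predict it. This stands as a warning about that score. It does not settle the value of other variables or of ward.
- **Covariates cost something.** With eight terms and R-squared 0.05, Phase II gains nothing (89.5% against 89.7%). This stands and argues for a short list.
- **The method is still open.** The tests are given as examples, to be used as appropriate, and Methods promises a full analysis plan before data are evaluated. That softens the point, but nothing in the supplied text provides for adjustment.

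A reader might also infer that the authors considered adjustment and rejected it because prediction is poor. The documents do not support this. The AUC is used to argue that all patients need continuous monitoring, and adjustment is never discussed.

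**Conclusion.** The point holds as a modest, inexpensive improvement. With four terms, the gain over the unadjusted test is about 0.7 points of power in Phase II and 1.0 in Phase III at R-squared 0.05, about 2.7 and 2.9 at 0.12, and about 6 at 0.25. The loss is under one point if the covariates are worthless. With seven terms, the Phase II loss in that case is 1.5 points (89.7% to 88.2%).

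These figures rest on a linear model for a mean difference, 1:1 allocation, SD units and an assumed R-squared. Durations are likely to be skewed, and the gain for a rank-based or proportional-odds analysis cannot be computed from the documents.

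Two stronger readings are tempting and should be resisted:

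- **That the primary test is wrong or the stated power mistaken.** Leaving out ward does not invalidate the test when randomization was not stratified by ward, and the power figures reproduce.
- **That adjustment would raise power to 93%.** That is the R-squared 0.12 result with no charge for estimating the covariates, and it rests on a different outcome.

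**What to change.** Before Phase II data are evaluated, prespecify one adjusted primary model for Phases II and III that still estimates a difference in time, for example a linear model on cumulative duration with robust variance.

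- Include treatment, ward and about three or four baseline terms. With more than two wards, keep the baseline terms to three.
- Choose the baseline terms for prognostic strength in the 100 blinded Phase I patients. Candidates are age, body mass index, COPD and current smoking. Previous participants are excluded from later phases, so this choice does not draw on the patients being compared.
- Add ward as a recorded field. Also name age explicitly, because Measurements does not list it separately.
- Keep the unadjusted t-test or Wilcoxon-Mann-Whitney test as a sensitivity analysis, and state which of the two it will be.

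The cost is SAP wording, one recorded field (plus age if it is not already captured) and a short look at Phase I data. No patients are added.
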